2. To provide a better foundation for the application of the PAL combined approach RARP.

III. Research Trial Management

The center will appoint one Principal Investigator overall, one Co-Investigator, and one Lead Statistician. Standardized statistical analysis methods will be applied. The trial will be conducted strictly in accordance with the protocol, ensuring the timely, accurate, and truthful completion

of case report forms. Researchers will receive training prior to the trial's initiation to familiarize themselves with the study protocol and unify assessment criteria.

Laboratory test reports must contain all essential items, including the date, test items, test results, and their normal reference ranges. A strict serious adverse event reporting system will be established.

If you have any questions regarding this study, you may contact the Principal Investigator.

Name	Role in Study	Phone Number
[name]	Principal Investigator	[name]
[name]	Investigator	[name]
[name]	Investigator	-
[name]	Investigator	-
[name]	Investigator	-

IV. Rationale for the Trial

1. Surgeons domestically and internationally have conducted in-depth research on various RARP approaches, such as the anterior, posterior, lateral, and transvesical approaches. However, each RARP approach has its own advantages and disadvantages.
2. Our center was the first in China to propose the PAL combined approach RARP in 2022. This approach involves initially using the posterior approach to separate the vas deferens, seminal vesicles, and Denonvilliers' fascia, followed by the anterior approach to separate the retropubic space, and then the lateral approach to separate the bladder neck and preserve the neurovascular bundles (NVB) as much as

possible. There are currently no prospective studies comparing this combined approach with other approaches.

V. Subject Selection and Withdrawal

(1) Inclusion Criteria:

Age \geq 40 years and \leq 80 years;

Patients diagnosed with prostate cancer by prostate biopsy;

Clinical T stage \leq T3a;

Full understanding of the clinical trial protocol and provision of signed informed consent.

Any outpatient or inpatient volunteer patient who meets all the above criteria can be enrolled as a subject.

(2) Exclusion Criteria:

Pre-existing urinary incontinence;

Previous endoscopic prostate surgery;

Presence of severe underlying diseases rendering the patient unable to tolerate surgery or with a life expectancy of < 5 years;

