Presence of metastatic disease or suspected lymph node involvement at diagnosis;

Patients deemed by the investigator as unsuitable for participation in this clinical trial.

Any patient meeting any of the above criteria cannot be enrolled as a subject.

(3) Discontinuation (Withdrawal) Criteria:

This refers to all patients who have signed the informed consent form, passed screening, and entered the trial but subsequently withdraw from the clinical trial.

Common reason: The patient requests to stop the trial.

When a patient discontinues, the investigator must record the reason for discontinuation in the case report form and complete all possible assessments and examinations, documenting the last condition, including the last trial-related procedures performed. For discontinuations due to adverse events, this must be recorded in the case report form, and the sponsor must be notified. Discontinued cases will be included in the analysis according to different scenarios.

VI. Study Protocol

Study Design

This is a prospective, randomized controlled, single-center clinical study. It primarily aims to compare the perioperative outcomes, pathological results, and early functional outcomes of PAL combined approach RARP and posterior approach (Retzius-sparing) RARP in the treatment of prostate cancer. All patients meeting the inclusion/exclusion criteria will be randomly assigned to one of two groups: the PAL combined approach group or the posterior approach group. This study plans to enroll no fewer than 30 patients per group.

Inclusion Criteria

Detailed inclusion and exclusion criteria are listed above. The key inclusion criterion is patients diagnosed with prostate cancer by biopsy and scheduled to undergo robot-assisted radical prostatectomy.

Randomization

Eligible subjects will be randomized in a 1:1 ratio to either the PAL combined approach group or the posterior approach group. The randomization process will be performed by an independent, dedicated statistician.

Surgical Methods

All patients will undergo surgery according to the standard procedures for robot-assisted radical prostatectomy.

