The primary observation indicator is the urinary continence rate after catheter removal. The urinary continence rate is defined as the number of patients with recovered continence per group divided by the total number of patients in that group. Urinary continence rates will be assessed at 1 day, 1 week, 3 months, 6 months, and 1 year after catheter removal. Recovery of urinary continence is defined as not using any pads or using only 1 safety pad per day with no leakage. Urinary incontinence is defined as using more than 1 pad per day. Immediate continence and early continence are defined as recovery of continence within 7 days and within 3 months after catheter removal, respectively.

Secondary Observation Indicators:

- (1) Perioperative indicators, such as: operative time, estimated blood loss, intraoperative and postoperative complications, time to drain removal, postoperative hospital stay;
- (2) Positive surgical margin status in the pathology report.

VIII. Ethical Requirements and Patient Informed Consent

This clinical trial will be conducted in accordance with the Declaration of

Helsinki (1996 version) and relevant Chinese regulations and guidelines for clinical trial research. The trial protocol must be approved by the Ethics Committee of each participating institution before the trial commences.

Before each patient is enrolled in this trial, the investigating physician is responsible for providing a complete and comprehensive explanation, in written form, to the patient or their designated representative, regarding the trial's purpose, procedures, and potential risks. Patients should be informed that they have the right to withdraw from the trial at any time. Each patient must be given a copy of the informed consent form before enrollment. The investigating physician is responsible for ensuring that each patient signs the informed consent form before entering the trial and for retaining the form in the study files.

IX. Statistical Analysis

Statistical tests will employ parametric methods or models wherever possible. All statistical tests for indicators will be two-sided, and a P-value ≤ 0.05 will be considered statistically significant.

Descriptive statistics for quantitative indicators will include the mean, standard deviation, median, and interquartile range. Descriptive statistics for categorical indicators will include counts and percentages. Statistical analysis will be performed using professional software such as SPSS, SAS, and R.

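### Does the gap between the continence and incontinence definitions, at one wet pad a day, leave the primary outcome undefined?

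*Protocol*

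**What the plan says.** Section VII of the protocol, under the primary observation indicator, sets the endpoint: "The primary observation indicator is the urinary continence rate after catheter removal". The rate is "the number of patients with recovered continence per group divided by the total number of patients in that group". The assessment times follow: "Urinary continence rates will be assessed at 1 day, 1 week, 3 months, 6 months, and 1 year after catheter removal". Two definitions then stand next to each other. The first is "Recovery of urinary continence is defined as not using any pads or using only 1 safety pad per day with no leakage". The second is "Urinary incontinence is defined as using more than 1 pad per day". Immediate and early continence are both built on recovery of continence, within 7 days and within 3 months of catheter removal.

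Section V (2) lists "Pre-existing urinary incontinence" among the exclusions. It gives no threshold and does not refer to Section VII. On size, Section VI says "This study plans to enroll no fewer than 30 patients per group", allocated 1:1.

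**The concern.** A reader expects continent and incontinent to cover every man between them. Here they do not. The first definition looks at pad count and leakage; the second looks at pad count alone. One pad a day with leakage is therefore not recovered under the first and not incontinent under the second. Both sentences sit in the primary endpoint paragraph, so an assessor asked for a yes/no status could defend either entry. The protocol describes no masking of assessors, and the trial is small, so a few such entries could move the comparison, possibly more in one arm than in the other.

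The same gap seems to reach eligibility. If the Section VII wording is carried back to Section V, a man who already wets one pad a day before surgery is not excluded, yet he fails the continence criterion before any operation. His outcome would then say little about the surgical approach.

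**Working it through.** **1. Classification.** Cross pads per day with leakage and apply each Section VII definition as written.

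| Pads per day | Leakage | Recovered continence? | Incontinent? |
|---|---|---|---|
| 0 | either | yes | no |
| 1 | no | yes | no |
| 1 | yes | no | no |
| 2 or more | either | no | yes |

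Exactly one combination falls in neither class: one pad with leakage.

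**2. What the primary rate does with that man.** The Section VII formula is

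rate = (men with recovered continence) / (all men in the group).

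Only the column for recovered continence enters the numerator. The man with one wet pad has "no" there, so he adds 0 to the numerator and 1 to the denominator. The incontinence column appears nowhere in the formula.

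**3. The rate before and after a repair.** Redefine incontinence as everything that is not recovered continence. Only the last column changes: the one-wet-pad row becomes "yes". The numerator and denominator in step 2 stay as they were, so the rate is identical in both arms at every assessment time.

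**4. Other uses of the incontinence sentence.** The secondary indicators in Section VII are perioperative measures and positive surgical margins. Immediate and early continence use recovery. No listed indicator is an incontinence rate.

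**5. What misclassification could do.** The protocol gives no frequency for one wet pad, so all counts here are assumptions. Section VI gives n = 30 per group as the minimum. One man is 1/30 = 3.3 points, three are 3/30 = 10 points and six are 6/30 = 20 points. Suppose that, against the formula, men with one wet pad are scored as continent:

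| Assumed counts out of 30 | Pearson chi-square P, uncorrected | Fisher exact P |
|---|---|---|
| 22 vs 15, by the formula | 0.063 | 0.110 |
| 25 vs 18, three moved in each arm | 0.045 | 0.084 |
| 25 vs 15, three moved in one arm only | 0.006 | 0.013 |

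The equal shift crosses 0.05 only with the uncorrected chi-square. With a continuity correction the first two rows give 0.111 and 0.086. The protocol names no test for the rates.

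Unequal shifts can go either way. By Fisher's test, 22 vs 13 (P = 0.035) becomes 24 vs 19 (P = 0.25) when 2 and 6 men are moved, and 18 vs 12 (P = 0.20) becomes 24 vs 15 (P = 0.029) when 6 and 3 are moved. Every moved row needs an assessor to depart from the formula in step 2.

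**6. Eligibility.** Section V excludes pre-existing incontinence in general terms. The Section VII definition belongs to an indicator measured after catheter removal. In the ordinary sense of the word, a man who leaks into a pad every day before surgery has incontinence and is excluded. Section V also excludes men whom the investigator considers unsuitable. Carrying the threshold of more than one pad back to baseline is a reading the text permits but does not state.

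**The case for a change.** The strongest case for a change runs as follows. The protocol itself fixes both definitions, in adjacent sentences, so the mismatch cannot be put down to detail left for an analysis plan. The incontinence sentence has no role in the formula, so its presence can only invite an assessor to use it. Section III promises training to unify assessment criteria, but training starts from the written criteria, and these leave one class unassigned. Any incontinence rate reported alongside the primary result would not be 100% minus the continence rate. The exclusion has no threshold, and the only written definition of incontinence in the document would admit a man who already fails the endpoint. A repair would take a sentence and a cross-reference.

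Much of this stands as comment on the drafting. The gap exists, an incontinence rate would not be the complement of the continence rate, and the exclusion carries no threshold. What does not stand is the step from there to the trial's result. The protocol says how the rate is formed and defines the one term it needs. Misclassification would be a departure from that text, and the absence of masking is a separate matter that this wording neither causes nor cures. The case report form is not shown, so whether pad count and wetness are already recorded separately cannot be judged. The number of men with one wet pad at baseline is unknown, and randomisation would spread them between the arms by chance.

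**Conclusion.** The two definitions in Section VII leave out the man with one wet pad a day, and that is a slip in wording. It does not leave his primary outcome open: by the protocol's own formula he is not continent, and the rate is the same whether or not the slip is corrected. The effect on the primary result, with the plan followed as written, is therefore zero. The shifts of 3.3 points per man, and the P-values that go with them, illustrate assessor error under assumed counts. The example with equal shifts in both arms is not significant by Fisher's exact test before (0.110) or after (0.084).

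The eligibility point rests on applying a postoperative definition to a baseline criterion that does not cite it, and the ordinary meaning of the exclusion already covers a man who leaks daily. An analyst who derives status from the recovery definition, and treats everyone else as not recovered, fills the gap correctly without an amendment. This conclusion assumes that the rate is computed by the stated formula and that no incontinence rate serves as an endpoint, which is how the protocol reads. No change to the plan follows.

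### Does the preference for parametric tests force underpowered t-tests onto skewed blood loss, drain time and hospital stay?

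*Protocol*

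**What the plan says.** Section IX (Statistical Analysis) gives one general rule for choosing tests: "Statistical tests will employ parametric methods or models wherever possible". It adds the significance criterion: "All statistical tests for indicators will be two-sided, and a P-value ≤ 0.05 will be considered statistically significant". It names no test for any outcome, does not define when a parametric approach counts as possible, and neither mentions nor excludes transformation or rank tests. For description it asks for both kinds of summary: "Descriptive statistics for quantitative indicators will include the mean, standard deviation, median, and interquartile range".

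The quantitative outcomes at issue are in the secondary list of Section VII (Observation Indicators), which gives as examples "operative time, estimated blood loss, intraoperative and postoperative complications, time to drain removal, postoperative hospital stay". The primary outcome in the same section is binary: "The primary observation indicator is the urinary continence rate after catheter removal".

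On size, Section VI (Study Design) says "This study plans to enroll no fewer than 30 patients per group", and under Randomization "Eligible subjects will be randomized in a 1:1 ratio to either the PAL combined approach group or the posterior approach group". No distribution, SD or expected difference is given for any perioperative outcome.

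**The concern.** The rule ranks parametric tests first by whether they can be done, not by whether the data suit them, and a t-test can be computed on any numeric variable. Blood loss, drain time, hospital stay and operative time cannot be negative, and a single complicated case can stretch each of them upwards. With about 30 patients per arm, a few such cases can move a mean and widen its interval.

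If these outcomes are log-normal and analysed untransformed, the cost can be real. At an assumed log-SD of 0.8 and a ratio of 1.7 between arms, power is 59% for the raw t-test, 68% for the rank-sum test and 71% for a t-test on logs. Perioperative outcomes come first in the objective in Section II, so missed differences there would matter. A mean-based test can also look out of step with a summary by median and interquartile range.

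**Working it through.** **Step 1: what the rule requires.** It allows parametric methods and parametric models. A t-test on log values is parametric, as are a log-normal and a gamma regression. The log-scale t-test, one of the two usual remedies for skew, therefore already complies. The harm arises only if the analyst chooses the untransformed t-test, which nothing in the protocol demands.

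**Step 2: the summary.** Section IX asks for mean and SD alongside median and interquartile range. A mean comparison matches the first pair and a rank comparison the second, so there is no mismatch.

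**Step 3: whether the raw t-test loses power.** The protocol states no power figure for these outcomes, so there is none to reproduce.

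Inputs from the protocol: 30 per arm (its minimum), 1:1 allocation, two-sided 0.05.

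Assumptions: the shape of the distribution, its spread and the effect.

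Reference point: the standardised difference detectable with 80% power is d = (1.960 + 0.842) × √(2/30) = 0.723. For log-normal data with log-SD s, the ratio between arms was set to exp(0.723 × s), so that the log-scale t-test has about 80% power. For s = 0.8 this is exp(0.579) = 1.78. The additive shifts were set to 0.723 SD on the raw scale.

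Each row rests on 20,000 simulated trials, so the simulation standard error at 70% power is √(0.7 × 0.3 / 20,000) = 0.3 points.

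| Assumed data | Raw t | Rank-sum | t on logs | Raw t minus rank-sum (points) |
|---|---|---|---|---|
| Log-normal, s = 0.3, ratio 1.24 | 77.4% | 76.5% | 79.2% | +0.9 |
| Log-normal, s = 0.5, ratio 1.44 | 74.4% | 76.6% | 79.3% | −2.2 |
| Log-normal, s = 0.7, ratio 1.66 | 69.3% | 76.0% | 78.8% | −6.7 |
| Log-normal, s = 0.8, ratio 1.78 | 66.4% | 75.9% | 78.3% | −9.5 |
| Log-normal, s = 1.0, ratio 2.06 | 60.6% | 77.0% | 79.2% | −16.4 |
| Log-normal, s = 1.2, ratio 2.38 | 53.4% | 76.2% | 79.2% | −22.8 |
| Log-normal, s = 0.5, additive shift | 79.1% | 90.3% | 93.2% | −11.2 |
| Log-normal, s = 0.8, additive shift | 81.3% | 98.6% | 99.4% | −17.3 |
| Gamma, shape 1, ratio 2.1 | 77.6% | 67.5% | 61.1% | +10.1 |
| Gamma, shape 2, ratio 1.7 | 80.2% | 73.5% | 71.6% | +6.7 |
| Gamma, shape 4, ratio 1.45 | 79.8% | 75.4% | 75.7% | +4.4 |
| Prolonged stays only, 2% vs 20% | 55.3% | 22.8% | 41.6% | +32.5 |

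Skewness alone does not settle the matter. Log-normal data with s = 0.5 have skewness (e^0.25 + 2) × √(e^0.25 − 1) = 1.8, and gamma data of shape 1 have 2/√1 = 2.0. The two are about equally skewed, yet with a ratio effect the raw t-test is 2.2 points behind the rank-sum test in the first case and 10.1 points ahead in the second.

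In the last row, most stays are about 6 days and a few last 15 to 20. If one approach simply produces more prolonged stays, the rank test is the one more likely to miss it.

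**Step 4: false positives.** Under no difference with log-normal data, the raw t-test rejects in 4.8% of trials at s = 0.3, falling to 3.7% at s = 1.2. It is somewhat conservative under heavy skew and never above the nominal level.

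**The case for a change.** The strongest counter-argument is that this is written text and not an omission. A later analysis plan would inherit a default that favours parametric tests without a distributional criterion, or would have to depart from it. The rule leaves raw t, log-scale t and gamma models all open. These differ in power and estimate different quantities, so a choice could be made after the data are seen. Marked log-normal skew is plausible for surgical blood loss and hospital stay. From s = 0.7 upwards the untransformed t-test loses about 7 to 23 points against the rank test with a ratio effect. With an additive shift the loss is already 11 points at s = 0.5.

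Those figures stand under their assumptions, and so does the remark that the condition for using a parametric test is undefined. Neither makes the rule wrong. An analysis plan that names a log-scale model for each outcome would carry out the rule, not contradict it. Naming the test per secondary outcome is work commonly left to that document, which may exist. That the best test depends on the unknown shape of the data also counts against treating rank or log-scale tests as the correct default.

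**Conclusion.** The concern does not hold. The rule does not impose raw-scale t-tests, one of the standard remedies already satisfies it, and the planned summaries fit either kind of test. The power loss depends on the assumed model. With 30 per arm it runs from nothing to about 23 points against the rank test under log-normal data with a ratio effect, and to about 17 points under the additive shifts shown. It becomes a gain of about 4 to 10 points under gamma data and of about 33 points when only the tail differs. The protocol contains nothing that selects among these cases.

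The primary continence outcome is untouched, type I error is not inflated, and 30 per group is a floor, not a fixed size. Choosing between means, logs and ranks for secondary perioperative outcomes is a trade-off on which experienced statisticians differ. The conclusion rests on reading the rule as written, with models included, and on the usual practice of fixing the test for each outcome in the analysis plan.

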X. Data Retention

The investigator shall retain all study documents, including identification of all participating subjects (enabling effective cross-referencing of different records, such as hospital source records), all original signed informed consent forms, and all case report forms, etc. The investigator shall retain the clinical trial data for 5 years after the completion of the clinical trial.

XI. Expected Timeline for the Clinical Trial

- (1) Trial preparation period: Month 1.
- (2) Clinical trial observation period: Months 2 – 8.
- (3) Data collection, statistical analysis, and summarization period: Months 8 -18.

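### The observation period in Section XI (Months 2 to 8) cannot hold the 1-year continence assessment, and the month-18 end holds it for every patient only if surgery stops by about month 6

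*Protocol*

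**What the plan says.** Section XI of the Protocol (Expected Timeline for the Clinical Trial) has three lines: "Trial preparation period: Month 1", "Clinical trial observation period: Months 2 – 8" and "Data collection, statistical analysis, and summarization period: Months 8 -18". Nothing is planned after month 18.

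Section VII defines the outcome: "The primary observation indicator is the urinary continence rate after catheter removal". The visit schedule is "Urinary continence rates will be assessed at 1 day, 1 week, 3 months, 6 months, and 1 year after catheter removal". The rate is the number of continent patients "divided by the total number of patients in that group".

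Section VI gives the size: "This study plans to enroll no fewer than 30 patients per group", so at least 60 patients.

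The Protocol gives no separate enrolment window, no date of last surgery and no catheter duration. It does not say that follow-up visits continue in Months 8 to 18.

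**The concern.** The Protocol fixes both a calendar and a visit schedule for its primary indicator, and for the 1-year visit the two do not fit. If the calendar were followed and the 1-year rate computed at month 18, one of two things would happen:

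- The rate would be computed only among patients operated on early enough. That is a smaller set than the whole-group denominator in Section VII, and it excludes everyone treated in the later months.
- The whole-group denominator would be kept. Patients not yet due for the visit would then count as not continent, and the rate would be understated in both groups.

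With about 30 patients per group, losing a substantial fraction at one time point matters for precision.

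**Working it through.** **Inputs.** Observation Months 2 to 8 and end at month 18 (Section XI); last visit 12 months after catheter removal (Section VII); at least 60 patients (Section VI). Catheter time *c* is not stated; 0 to 14 days is assumed, that is 0 to 14/30.44 = 0.46 months.

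**Time axis.** Month *k* runs from *k* − 1 to *k* elapsed months. The start of month 2 is 1.0, the end of month 8 is 8.0 and the end of month 18 is 18.0.

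**Step 1: the observation period as written.** Its length is 8 − 1 = 7 months counted inclusively, or 8 − 2 = 6 by subtraction. Either is shorter than 12. The earliest possible 1-year visit is 1 + *c* + 12 = 13.0 to 13.5. No patient can have it by 8.0, whatever the accrual or catheter time. On this literal reading even the 6-month visit fits only for catheters removed by 8 − 6 = 2.0, the end of month 2.

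**Step 2: Months 2 to 8 read as the surgery window, follow-up continuing in Months 8 to 18.** For surgery at 8.0:

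| Visit | Formula | Elapsed months | By 18.0? |
|---|---|---|---|
| 3 months | 8 + *c* + 3 | 11.0 to 11.5 | yes |
| 6 months | 8 + *c* + 6 | 14.0 to 14.5 | yes |
| 1 year | 8 + *c* + 12 | 20.0 to 20.5 | no |

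If surgery stops at the start of month 8 (7.0), the last 1-year visit is at 19.0 to 19.5, still too late. The latest surgery that allows a 1-year visit by 18.0 is at 18 − 12 − *c* = 6.0 to 5.5.

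**Step 3: share without a 1-year visit at 18.0.** With uniform accrual from *s* to *A*, the share is 1 − (6 − *c* − *s*)/(*A* − *s*).

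| Reading | *s*, *A* | Share lacking | Of 60 |
|---|---|---|---|
| Surgery to the end of month 8 | 1, 8 | 1 − 5/7 to 1 − 4.54/7 = 29 to 35% | 17 to 21 |
| Surgery to the start of month 8 | 1, 7 | 1 − 5/6 to 1 − 4.54/6 = 17 to 24% | 10 to 15 |
| Month labels read as time points | 2, 8 | 1 − 4/6 to 1 − 3.54/6 = 33 to 41% | 20 to 25 |
| All surgery done by about 5.5 | 1, 5.54 | 0% | 0 |

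In the first row, about 30 × 0.71 = 21 to 30 × 0.65 = 19 patients per group would have 1-year data. If the whole-group denominator were kept, the reported 1-year rate could not exceed about 65 to 71%, even if every assessed patient were continent.

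**Step 4: what the 0% case requires.** Starting at 1.0, 60 operations in 5.0 to 4.54 months is 12 to 13 per month, against 60/7 = 8.6 over the full window, and no analysis time remains. Keeping 2 months for analysis needs 60/3.0 to 60/2.54, or 20 to 24 per month.

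**The case against.** The best case for the Protocol is that Section XI is headed as an expected timeline, and so is a forecast. Its third period includes data collection, which suggests that outcomes are still being gathered after month 8. On that reading the 7-against-12-month conflict is loose labelling, and the overrun depends on a last-surgery date that the Protocol does not give. Nothing says that follow-up stops or data are cut at month 18, and a rule for the data cut may properly sit in a statistical analysis plan. The aim is early function, with early continence defined as recovery within 3 months, so only the last of five time points is at risk.

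Much of this stands. The overrun is conditional, a biased 1-year rate is a risk and not a certainty, and the absence of a data-cut rule is not itself a fault of the Protocol. The percentages depend on the assumptions: accrual weighted to later months would exceed them, and 21 catheter days would raise the time-point reading to 1 − 3.31/6 = 45%. On that same reading, the rate for the 0% case would be 60/4.0 to 60/3.54, or 15 to 17 per month.

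The mismatch remains. The generous reading works for the 1-year visit only if the last catheter is removed by the end of month 6. The Protocol states no such limit, and it would use up all the time that the same line reserves for analysis.

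**Conclusion.** The point holds. That no 1-year assessment can fall within Months 2 to 8 follows from the Protocol's own figures without any assumption. That the last 1-year visits fall after month 18 is conditional on surgery continuing beyond about 5.5 to 6.0 elapsed months. If it runs to the end of month 8, the last visit is 2.0 to 2.5 months late and 29 to 35% of patients lack it at month 18. The scenarios tabulated run from 0% to about 41%, all under assumed uniform accrual, 60 patients and 0 to 14 catheter days.

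This is a planning inconsistency that should be corrected. It does not touch the assessments up to 6 months if Months 2 to 8 are the surgery window.

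**What to change.** Reconcile Section XI with Section VII by stating three separate periods:

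1. Recruitment and surgery, with a last-surgery date. If Months 2 to 8 are meant, say so.
2. Follow-up until the last patient's 1-year assessment. This runs into month 21 if surgery continues to the end of month 8.
3. Data lock and analysis after that.

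State, in the Protocol or the statistical analysis plan, that the 1-year rate is analysed only once every patient has reached that visit or left the study before it.

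The cost is a timeline amendment and a final 1-year report several months later. No extra patients or visits are needed. Results up to 6 months could still be ready within the 18 months, since the last 6-month visit falls at about 14.5.
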